Platelets-Rich-Plasma group: Patients will be asked to stop taking any type of anti-inflammatory medication from 7 days before the procedure to 2 weeks after. At the moment of the procedure, at CMC, the radiology team will draw 30cc of venous blood from the patient and the blood will be processed with the PRP kit and centrifuged in the SmartPrep PRP machine.. The patient is then scanned prone using a linear 14 or 9 MHz transducer. A 20 Gauge spinal needle is usually employed for purposes of aspiration. We can use sterile saline to confirm needle placement in the cyst in lieu of lidocaine and then inject the PRP by the radiologist.

The procedure will be done without using any local anesthetic to avoid pharmacological interaction with the injected substance. A compression bandage will be placed locally for 7 days. Investigators will monitor any side effect from the injection and treat the patients per standard care, this can include

prescription of analgesics. No remaining biomaterial or any blood sample will be collected or stored for future studies.

It must be noted that the radiology team (technicians and radiologist) in charge of the PRP processing and handling, are well trained in this matter, since they have been using PRP and Harvesttech SmartPrep PRP machine in a weekly and sometimes daily basis, as part of patient's treatment or as part of previous clinical trials. [name], who is one of the Co-investigators, will be the radiologist supervising the study in the radiology department, to minimize any potential risk, and assuring appropriate preparation of the product and execution of the procedure.

**Corticosteroid group:** Patients will be asked to stop taking any kind of anti-inflammatory medication from 7 days before the procedure to 2 weeks after.. The radiology team will draw 30cc of blood from the patient, and this blood will then immediately be discarded out of sight from the patient. The blood does not need to be used for the control group, and none of it will be stored for future use. Blood draw is crucial in this group as it will keep the research activities consistent between the groups and prevent any patient from knowing if they are in the treatment or control group. It is crucial to keep the patient blinded for the study to eliminate any bias in the outcomes.

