## III. Data Safety Monitoring Plan (DSMP)

### I. Description of the types of data or events that will be captured

#### a. SAFETY information to be collected

All disease signs and symptoms experienced by the patient, as defined below as AE, TEAE, SAE, and UADE, will be recorded from questionnaires during each visit and clinic visits. Specific information collected about the adverse event will include the nature, date and time of the event. There will also be a determination of seriousness, frequency, severity, corrective treatment, outcome, and the principal investigator's opinion of the relationship to the Ultrasound guided aspiration and injection of either Corticosteroid or Platelet-Rich-Plasma. Documentation will begin at the time the patient signs the informed consent form to the completion of the final study visit.

- Adverse Event (AE)

An AE is any untoward or unfavorable medical occurrence in a patient involved in a study associated with the use of a medical treatment or procedure regardless of whether it is considered related to the treatment or procedure. AEs therefore include any undesirable physical, psychological or behavioral effect experienced by a subject during their participation in this investigational study, whether or not the effect is considered interrelated.

The Principal Investigator will assess relationship between the AE and study treatment according to the following definitions:

- Unrelated: There is no relationship between the AE and the use of the investigational device or any study treatment. This may include but is not limited to the incident being an expected outcome of a previously existing or concurrent disease, concomitant medication or procedure the patient experienced.
- Remote/unlikely: There is no clear relationship between the AE and the use of the device under investigation or study treatment and it is unlikely that there is some relationship.
- Possible: There is no clear relationship between the AE and the use of the study device or study treatment; however, one cannot definitely conclude that there is no relationship.

- Probable: While a clear relationship to the device under investigation or study treatment cannot be established, the AE is associated with an expected AE or there is no other medical condition or intervention, which could explain the occurrence of such an event.

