## 5. RISKS AND BENEFITS

### I. Risks:

Subjects involved in the study will be at risk of complications associated with the injection such as pain at the site of the injection, infection, bleeding or hematoma formation.

Subjects in the Corticosteroid group: Studies have shown that corticosteroid injection into soft tissues is safe, and no serious unexpected reactions have been reported. In general, corticosteroid injection into the cyst may result in local atrophy and post injection flare but the use of Triamcinolone lowers the frequency of these complications from happening due to its pharmacological characteristics.

Subjects in the PRP group: Although There has been no data about using PRP into a baker's cyst, studies have stated that the side effects of Platelets-Rich-Plasma injections in soft tissues are very limited as the patients are utilizing their own blood. The main risk includes local infection (less than 1%) and flare reaction beginning the day after the injection.

Breach of confidentiality is an unlikely, but possible risk to subjects included in this study.

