### II. Protection Against Risks:

Medical protection for Corticosteroid group: Studies have reported that the use of triamcinolone acetonide and its dilution with lidocaine without epinephrine decrease the risk of local atrophy and post injection flares. Study investigators will monitor any side effect from the injection and treat them per standard practice. This can include prescription of oral anti-inflammatory medications or analgesics, provision of counseling for self-management by the patient and referral for further treatment as necessary.

Medical Protection for PRP group: The study investigators will monitor the patients and any side effect from the injection and treat them as necessary, including the prescription of analgesics, provision of counseling for self-management by the patient and referral of the patient for further treatment if needed.

All patients will be deidentified and given a code. Information linking the patient codes to the participants' names and medical record numbers will be stored in a secure location separate from the medical information. Access to the information linking the linkage codes with participant identifiers shall be documented.

Participant medical information will be stored electronically within a password protected spreadsheet available only to the PI, co-investigators, and research staff as necessary for data analysis. The names and medical record numbers of the study participants will be deleted from their stored medical information and replaced with a linkage code. Access to participant medical information contained within the registry will be restricted.

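### The risk section allows oral anti-inflammatories for corticosteroid-arm side effects with no time limit, although the Methods ask both arms to avoid them until two weeks after the procedure (low priority)

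*Combined protocol and SAP*

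**What the plan says.** In the combined protocol and SAP, section 4 (Methods and procedures), the corticosteroid paragraph states: "Patients will be asked to stop taking any kind of anti-inflammatory medication from 7 days before the procedure to 2 weeks after". The PRP paragraph sets the same window: "Patients will be asked to stop taking any type of anti-inflammatory medication from 7 days before the procedure to 2 weeks after". For side effects, the same section tells investigators in each arm to give standard care and names analgesics as an example. It names no anti-inflammatory in either arm.

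Section 5, II (Protection Against Risks) covers side-effect treatment again, arm by arm. For the corticosteroid group: "This can include prescription of oral anti-inflammatory medications or analgesics". For the PRP group, investigators are to "treat them as necessary, including the prescription of analgesics". Neither paragraph mentions the two-week stop.

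Section 5, I (Risks) expects a flare in both arms. For the corticosteroid group, "corticosteroid injection into the cyst may result in local atrophy and post injection flare". For PRP it lists a "flare reaction beginning the day after the injection".

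The Data Safety Monitoring Plan records adverse events in some detail: "Specific information collected about the adverse event will include the nature, date and time of the event", and "There will also be a determination of seriousness, frequency, severity, corrective treatment, outcome". Aims 3 and 4 (section 2, IV) are to evaluate complications and side effects.

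**The concern.** The protocol gives two accounts of how corticosteroid-arm side effects may be treated. One of them permits a drug class that the same arm is asked to avoid for two weeks after the injection. The permission is written for one arm only, although the stop applies to both.

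The comparison of side effects is what is at stake. The severity and outcome of each event are to be recorded. Suppose an early flare after corticosteroid is treated with an anti-inflammatory and an early flare after PRP with a simple analgesic. If the anti-inflammatory helps the flare settle, the corticosteroid arm's events could be recorded as milder or shorter for a reason unrelated to the injected product.

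**Working it through.** No figure in the plan bears on this point, and the sample size of 25 per arm does not enter. The check is a comparison of texts plus one calculation of dates.

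**Step 1: the rules side by side.**

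| Rule | Corticosteroid arm | PRP arm |
|---|---|---|
| Anti-inflammatory stop (section 4) | 7 days before to 2 weeks after | 7 days before to 2 weeks after |
| Side-effect treatment named in section 4 | Analgesics | Analgesics |
| Side-effect treatment named in section 5, II | Oral anti-inflammatories or analgesics | Analgesics |
| Flare expected (section 5, I) | Yes, no date given | Yes, from the day after injection |

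The first two rows agree across arms. The third differs across arms and, for the corticosteroid arm, also differs from the first two.

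**Step 2: where the rules overlap.** With the procedure on day 0, the stop runs from day −7 to day 14. The permission in section 5, II has no end date and starts with the first side effect, so it can apply from day 0. The overlap is days 0 to 14. An oral anti-inflammatory prescribed in that period follows section 5 and breaks the stop in section 4. After day 14 there is no conflict.

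**Step 3: distance from the outcome visits.** The schedules place follow-up at weeks 12 and 24.

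- Week 12: 12 × 7 − 14 = 70 days after the stop ends.
- Week 24: 24 × 7 − 14 = 154 days after the stop ends.

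A short course in the first two weeks is therefore remote from the VAS, KOOS, Rauschning and Lindgren, and ultrasound assessments. Side effects themselves can fall inside the window.

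**Step 4: whether the use can be traced.** Adverse events carry a date and a corrective treatment. Prescribed anti-inflammatory rescue for an event dated within the window can be counted by arm without new data. The recorded date is that of the event, not of the prescription, so events late in the window may be misplaced by a few days.

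**Step 5: the seven days before the procedure.** Both schedules mark informed consent and the aspiration with injection under the same Visit 1. The eligibility lists do not mention anti-inflammatory use, so current users can enrol. One who is consented and treated on the same day cannot complete a seven-day stop after consent. The narrative in section 4 does not require this. Its same-day wording attaches to the baseline questionnaires, the procedure is described separately with the radiology team, and follow-up is counted from the procedure day.

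**The case against.** The strongest reply is that this is a drafting mismatch with no contradiction in practice. The operational text in section 4 already treats the arms alike. The stop is a request about what patients take, while section 5 is a permissive statement about what an investigator may prescribe. Both can be honoured by using analgesics up to day 14 and either class afterwards, or section 5 can be read as an unwritten rescue exception. Most of this stands, and it is why the priority is low. What remains is that no exception or time limit is written down, and the drug class is named for one arm only.

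Three stronger readings are tempting, and the documents do not support them.

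- A reader might infer that PRP patients are barred from anti-inflammatory rescue. The PRP wording is open-ended and gives analgesics as an example. The arms differ in what is named, not in what is forbidden.
- A reader might infer that corticosteroid flares are known to fall inside the two weeks. Only the PRP flare is dated. An early corticosteroid flare is plausible, but its timing is not stated, and section 5 says that the choice and dilution of triamcinolone make flares less frequent.
- A reader might infer from the schedules that the seven-day stop is impossible. They show no interval, but the narrative allows a later procedure day. This is an ambiguity in the schedule, and it is the same in both arms.

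**Conclusion.** The inconsistency is real and narrow. For days 0 to 14 in the corticosteroid arm, section 5, II permits what section 4 asks patients to avoid, and it departs from the analgesic wording that section 4 gives to both arms. Early co-treatment could therefore differ by arm, which bears mainly on Aims 3 and 4.

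A reader might go further and infer bias in the efficacy comparison. That is not supported. The stop ends 70 and 154 days before the outcome visits, and the protocol gives no expected number of side effects treated with anti-inflammatories. Any effect on those outcomes cannot be sized from the documents and is probably small. The conclusion for Aims 3 and 4 assumes that some side effects are treated within 14 days and that staff may act on the risk section.

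The schedule point is minor and does not bias the comparison. Overall priority: low.

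**What to change.** Amend both paragraphs of section 5, II so that they carry the same rule: until two weeks after the procedure, treat side effects with analgesics that are not anti-inflammatory, unless an anti-inflammatory is medically necessary. In the analysis, report anti-inflammatory use within that window by arm, from the adverse-event date and corrective treatment already collected. The cost is a wording change and one tabulation. No needed care is withheld, and the sample size and outcome measures stay as they are.

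As a minor addition, state with the schedules that patients who took an anti-inflammatory in the previous 7 days have the procedure at least 7 days after enrolment. Others may be treated on the enrolment day. For the patients affected, this means about a week's delay, possibly a second trip, and baseline scores taken before the procedure day.

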**1. BRIEF SUMMARY**

Baker's cyst is a common entity in adults who have knee pathologies, having different ways to approach it with different recurrence rates. We will attempt to report the outcome of treating Baker's cysts with ultrasound-guided Platelets-Rich-Plasma injection into the cyst versus ultrasound guided Corticosteroid injection into the cyst with at least 6 months follow-up. We plan on evaluating recurrence rates and persistence of symptoms.

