#### VI. **Exclusion criteria**

- Patients younger than 18 years old
- Local or Systemic active infection

- Active cancer treatment
- Immunodeficiency
- Diabetes
- Hypersensitivity or allergy to Corticosteroid or Lidocaine

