**4. METHODS AND PROCEDURES****I. Methods and procedures**

Patients who meet the inclusion criteria and do not meet any of the exclusion criteria will be identified during office hours by the PI and co-investigators. Our research staff will explain the purpose of the study to the patient, and will go over the consent form, to fully inform and answer any questions the subject may have.

After patients accept to participate in the study and are formally enrolled in the study, the same day, patients will be asked the Visual Analogue Score (VAS), demographic information will be collected, along with any associated medical history with special interest in knee pathologies and previous treatments. They will be also classified according to their symptoms by the Rauschning and Lindgren criteria which are used to clinically evaluate the presence of the popliteal cysts, pain, posterior sense of tension in the popliteal fossa and its clinical importance for range of motion reduction. They will also complete the Knee Injury and Osteoarthritis Outcome Score (KOOS) to assess short and long term outcome of knee related conditions.

Rauschning and Lindgren criteria:

Grade 0: absence of swelling and pain, no limitation of range of motion

Grade 1: light swelling or a sense of posterior tension after intense activity, minimal limitation of ROM

Grade 2: swelling and pain after normal activity, ROM limitation less than 20 degrees

Grade 3: swelling and pain even when resting, ROM limitation more than 20 degrees

The Knee Injury and Osteoarthritis Outcome Score (KOOS):

- Pain
- Other Symptoms
- Function in daily living (ADL)
- Function in sport and recreation
- Knee-related quality of life (QOL)

We will blindly set 25 envelopes sealed for each group, and randomly assign one of them to each patient. Patients will then be part of either the Platelets-Rich-Plasma group or the Corticosteroid group.

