An ultrasound guided aspiration and triamcinolone (40 mg) diluted with lidocaine without epinephrine and ropivacaine will be used to anesthetize the tissues down to the cyst(including within the cyst for steroid injections). A compression bandage will be placed locally for 7 days. Investigators will monitor any side effect from the injection and treat the patients per standard care, this can include prescription of analgesics.

Both groups will be asked to have a follow up after 3 months and 6 months of the day of the procedure with measurements of the dimensions of the baker's cysts with ultrasound, Visual Analogue Score, and Rauschning and Lindgren criteria and reclassification.

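### The corticosteroid-arm injectate appears to include ropivacaine, but the allergy exclusion covers only corticosteroid and lidocaine

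*Combined protocol and SAP*

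**What the plan says.** Section 4.I of the combined protocol and SAP describes the corticosteroid procedure in one sentence: after ultrasound-guided aspiration, "triamcinolone (40 mg) diluted with lidocaine without epinephrine and ropivacaine will be used to anesthetize the tissues" on the way to the cyst. A parenthesis in the same sentence adds that, for steroid injections, this extends to the inside of the cyst.

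Section 3.VI (Exclusion criteria) has one allergy item: "Hypersensitivity or allergy to Corticosteroid or Lidocaine". The other items are age under 18, active infection, active cancer treatment, immunodeficiency and diabetes.

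Section 5.II (Protection Against Risks) reports that, according to studies, "the use of triamcinolone acetonide and its dilution with lidocaine without epinephrine decrease the risk of local atrophy and post injection flares". Section 5.I (Risks) says that "corticosteroid injection into the cyst may result in local atrophy and post injection flare". Neither section mentions ropivacaine, and section 5.I names no local-anesthetic risk for the corticosteroid group.

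For the PRP arm, section 4.I says: "The procedure will be done without using any local anesthetic to avoid pharmacological interaction with the injected substance".

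**The concern.** The plan already treats allergy to an injected agent as a reason to exclude, and it names two such agents. If a third is injected, the list is incomplete by the plan's own logic. An investigator who follows the criteria to the letter would enrol a patient known to be allergic to ropivacaine, and the envelope could then assign that patient to the arm that uses it.

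What is at stake is patient safety and the clarity of a treatment instruction, not the trial's statistical answer. If the allergy came to light only after assignment, the protocol does not say what should happen, so the choice would be made case by case.

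**Working it through.** The plan states no figure on this point, so there is none to reproduce. The check is a comparison of the text, followed by a short calculation of size.

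**Step 1: agents given against agents screened (ordinary reading)**

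| Agent | Named in the corticosteroid procedure (4.I) | Named in the allergy exclusion (3.VI) | Named in the risk text (5.I, 5.II) |
|---|---|---|---|
| Corticosteroid (triamcinolone) | Yes | Yes, as a class | Yes |
| Lidocaine | Yes, without epinephrine | Yes | Yes, without epinephrine |
| Ropivacaine | Yes | No | No |

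Ropivacaine appears once in the whole document, in the corticosteroid procedure.

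**Step 2: does any other criterion close the gap?** None of the listed exclusions is general. There is no item for local anesthetics as a class, for a contraindication to any study agent, or for the investigator's judgement. The inclusion criteria ask only for age of at least 18 and a symptomatic cyst. A patient allergic to ropivacaine alone therefore meets no exclusion.

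**Step 3: how sure is the reading?** The phrase can be parsed in two ways.

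- Reading A: the missing epinephrine describes the lidocaine, and ropivacaine is a further diluent. This is the ordinary reading. Section 5.II uses the same qualifier in the same way: "the use of triamcinolone acetonide and its dilution with lidocaine without epinephrine".
- Reading B: both epinephrine and ropivacaine are left out. This would agree with section 3.VI and with the silence of sections 5.I and 5.II.

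Under A there is a gap in screening. Under B there is none, but a treatment instruction can be taken either to include or to omit a drug. Both call for a change to the text.

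**Step 4: who could be exposed?** Eligibility is settled before assignment. On allocation, section 4.I says: "We will blindly set 25 envelopes sealed for each group". With 25 envelopes per arm and 50 in total, the chance that any one patient draws corticosteroid is 25/50 = 0.5. The PRP arm uses no local anesthetic, so exposure arises only in the corticosteroid arm.

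Let p be the share of enrolled patients with known ropivacaine hypersensitivity and no known lidocaine or corticosteroid allergy. The expected number exposed, if nothing else intervenes, is 50 × p × 0.5 = 25p. The documents give no value for p. For the expected number to reach one, p would have to be 1/25 = 0.04, that is, 4% of those enrolled. For any smaller p the expected number is below one.

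**The case against.** The strongest reply is that this is a wording mismatch with little practical reach. Reading B is possible and fits the rest of the document. The schedules of events place a complete physical and medical history at baseline, the same visit as the injection, and a named co-investigator radiologist supervises the procedure to limit risk. A known allergy might well be caught. The consent pages are not part of the available text, so they may mention ropivacaine.

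Much of this stands as mitigation. It does not remove the point. Section 4.I has the history taken after formal enrolment, with its stated focus on knee pathology and earlier treatment, and neither the history nor the supervision makes this allergy a ground for exclusion. Reading B, if intended, moves the fault from section 3.VI to section 4.I.

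Two stronger readings are tempting, and the documents do not support them.

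- A reader might infer that section 5.II specifies a different injectate from section 4.I. It reports what studies found about a lidocaine dilution and is silent on ropivacaine. Only section 4.I specifies what this trial injects.
- A reader might infer that the procedure contradicts the Brief Summary, which speaks of "ultrasound guided Corticosteroid injection into the cyst", because section 4.I refers to the tissues leading to the cyst. The parenthesis in section 4.I places the steroid inside the cyst, in agreement with both the Brief Summary and section 5.I. The sentence is clumsy, but no conflict over the injection site is shown.

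**Conclusion.** The point holds in a limited form. On the ordinary reading of section 4.I, the corticosteroid arm uses an agent that the hypersensitivity exclusion does not cover, so a patient with known allergy to that agent alone is eligible and may be assigned to receive it. On the other reading, section 4.I is ambiguous about what is injected. One of the two must be true, and each needs correcting.

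It would go too far to say that such a patient will receive ropivacaine, since assignment to that arm has probability one half. It would also go too far to say that all 25 corticosteroid patients are affected, since the gap matters only to someone with this particular allergy history. The number is unknown and probably very small. Sample size, power and analysis are unaffected.

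The conclusion assumes that the listed exclusion criteria are the complete set applied at screening. It does not depend on which agents the sponsor intended. The case for acting is that the gap concerns an avoidable harm and costs almost nothing to close.

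**What to change.** Reconcile sections 3.VI and 4.I so that the agents given in the corticosteroid arm and the agents covered by the hypersensitivity exclusion match, whichever agents the sponsor confirms. Reword the sentence in section 4.I so that it can be read in only one way on ropivacaine. Bring the risk text in sections 5.I and 5.II into line with the result, and check that the consent form agrees.

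The cost is a one-line amendment to the protocol and the screening form, with small matching edits to the risk text. The effect on recruitment should be negligible, and nothing in the design or analysis changes.
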